#### **Appendix 4: Determining Hypoglycemic and Hyperglycemic Episodes**

For this study, a subject will be described as having hypoglycemic or hyperglycemic episodes when the following definitions are met:

- Documented Symptomatic Hypoglycemia is defined as an event during which typical symptoms of hypoglycemia are accompanied by a measured plasma glucose concentration  $\leq 70$  mg/dl.
- Asymptomatic Hypoglycemia is defined as an event not accompanied by typical symptoms of hypoglycemia but with a measured plasma glucose concentration  $\leq 70$  mg/dl.
- Probable symptomatic hypoglycemia is defined as an event during which symptoms of hypoglycemia are not accompanied by a plasma glucose determination, but that was presumably caused by a plasma glucose concentration  $\leq 70$  mg/dl.
- Relative Hypoglycemia is defined as an event during which the person with diabetes reports of the typical symptoms of hypoglycemia, and interprets those as indicative of hypoglycemia, but with a measured plasma glucose concentration  $> 70$  mg/dl.
- Severe Hypoglycemia is defined as an event requiring assistance of another person to actively administer carbohydrate, glucagons, or other resuscitative actions, or when a measured plasma glucose concentration is  $< 40$  mg/dl.
- Hyperglycemia is defined as plasma glucose level  $> 140$  mg/dl.
- Severe hyperglycemia is defined as plasma glucose level  $> 300$  mg/dl.

\* *Definitions of hypoglycemic episodes were defined per "Defining and Reporting Hypoglycemia: A report from the American Diabetes Association Workgroup on Hypoglycemia" from May, 2005 issue of Diabetes Care.*

### Document Version History

Version	Date	Author	Description of Changes
1.0	21 June 2017	[name]	Initial version
1.1	29 August 2017	[name]	Modified the following by sponsor request. 1. Added exploratory efficacy analysis for TAFGC. 2. Added paired t-test (or Wilcoxon signed-rank test) to analysis the change of efficacy endpoints within each group. 3. Deleted Analysis for unexpected adverse events.
1.2	16 October 2017	[name]	Modified the following by sponsor request. 1. Added 1 exploratory efficacy endpoint – BMI. 2. Added exploratory efficacy analyses for BMI. 3. Updated calculation for TAFGC. 4. Added sponsor defined definitions for Hypoglycemia and Hyperglycemia 5. Added section for Subgroup Analysis. 6. Added section for Post-hoc Analysis.

**Table of Abbreviations**

Abbreviation	Description
AE	Adverse Event
ADDQoL	Audit of Diabetes-Dependent Quality of Life
BMI	Body Mass Index
BP	Blood Pressure
BSA	Bio-Statistics Associate
BSM	Bio-statistics Manager
BW	Body Weight
cGMP	Current Good Manufacturing Practice
CHP	Cyclo (His-pro)
CRO	Contract Research Organization
CTCAE	Common Terminology Criteria for Adverse Events
Cyclo	Cyclic dipeptide
DBMS	Database Management System
DM	Diabetes Mellitus
DPP	Dipeptidyl Peptidase
DW	Distilled Water
eCRF	Electronic Case Report Form
EAS	Efficacy Analysis Set
EDC	Electronic Data Capture
FAS	Full Analysis Set
FDA	Food and Drug Administration
FPG	Fasting Plasma Glucose
GCP	Good Clinical Practice
G-K	Goto-Kakizaki
GLP	Good Laboratory Practice
GLP-1	Glucagon-like protein-1
GLUT-4	Glucose transporter-4
GMP	Good Manufacturing Practice
HbA1c	Hemoglobin A1c
hCG	human chorionic gonadotropin
IB	Investigator's Brochure
ICF	Informed Consent Form
ICH	International Conference on Harmonization
IDE	Insulin Degrading Enzyme
IEC	Independent Ethics Committee
IP	Investigational Product
IRB	Institutional Review Board
LOCF	Last Observation Carried Forward
MedDRA	Medical Dictionary for Regulatory Activities
MsSQL	Microsoft Structured Query Language
NIDDM	Non-insulin-dependent Diabetes Mellitus
ODBC	Open Database Connectivity
OGTT	Oral Glucose Tolerance Test
PT	Preferred Term

---

SAE	Serious Adverse Event
SAP	Statistical Analysis Plan
SD	Standard Deviation
S-D	Sprague-Dawley
SEM	Standard Error of the Mean
SMC	Safety Monitoring Committee
SOC	System Organ Class
SOP	Standard Operating Procedure
TAFGC	Three-hour-area-average Above Fasting Glucose Concentration
TSH	Thyroid Stimulating Hormone
T3	Triiodothyronine
T4	Thyroxine
WHODRUG	World Health Organization Drug

## 1. INTRODUCTION

This Statistical Analysis Plan (SAP) is developed to guide the details of the statistical analysis method of the phase 2 study to evaluate the efficacy and safety of Cyclo-Z in patients with obese type 2 diabetes. The SAP includes detailed definitions of the populations to be analyzed, the subject characteristics and the efficacy and safety endpoints, as well as the specific statistical analysis methods to be performed.

## 2. STUDY OBJECTIVE(S)

### 2.1 Primary Objective

The primary objective is to assess the dose-dependent efficacy of Cyclo-Z for the treatment of subjects with obese type 2 diabetes.

### 2.2 Secondary Objective

The secondary objective is to assess the safety of Cyclo-Z in the treatment of subjects with obese type 2 diabetes.

## 3. STUDY OVERVIEW

### 3.1 Study Design

#### 3.1.1 Overall Study Design

This is a double-blind, randomized, placebo-controlled, parallel-group comparison study to evaluate the efficacy and safety of Cyclo-Z vs. placebo in adult subjects with obese type 2 diabetes. Up to four sites may be utilized in the United States so that a total of 80 subjects (a potential 20% screening failure rate) may be screened for total 16-week study period (2 weeks for screening, 12 weeks for treatment, and 2 weeks for safety follow-up).

Subjects who meet preliminary inclusion and exclusion criteria at Screening will undergo a 2-week assessment period of record-keeping compliance. Subjects will be asked to record daily blood glucose values (fasting before breakfast and two hours after dinner) and study medication adherence throughout study participation.

Sixty-four (64) qualified subjects will be assigned randomly to either the placebo arm or to one of the three treatment groups requiring the oral intake of a single gel capsule of Cyclo-Z or placebo once daily before bedtime for 12 consecutive weeks.

Refer to the schedule of assessment of [Section 3.1.2](#) for a display of all assessments to be conducted. All visits are to be scheduled according to their time from the randomization visit (Visit 2).

3.1.2 Schedule of Assessment

Study Visits 	Screening	Treatment Period							Follow-up
	V1	V2	V3	V4	V5	V6	V7	V8	V9
	Screen (Week -2)	Baseline (Week 0)	Week 2	Week 4	Week 6	Week 8	Week 10	Week 12	Week 14
Informed Consent	X								
Inclusion/Exclusion Criteria	X	X							
Demographic (including height)	X								
Medical/Medication History	X								
Physical Examination	X	X		X		X		X	
Vital Signs and Body Weight	X	X	X	X	X	X	X	X	X
12-lead ECG	X							X	
Blood Sampling for serum chemistry, hematology, FPG, HbA1c, hCG, TSH, T3, and T4 	X	X		X		X		X	
Blood Sampling for zinc, insulin, adiponectin, C-peptide, leptin, glucagon, [CHP in a subset of subjects 		X		X		X		X	
Urine Sampling for glucose, microalbumin, copper, and zinc		X		X		X		X	
Dispense and Review Daily Log	X	X	X	X	X	X	X	X	
Dispense and Review Medications		X	X	X	X	X	X	X	
Waist Circumference		X		X		X		X	
OGTT 		X						X	
ADDQoL Questionnaire		X						X	
Review of Adverse Event and Concomitant Medication 		X	X	X	X	X	X	X	X

- 1) Visits 3 to 8 have ±3 day visit window and Visit 9 has +7 day visit window.
- 2) Serum chemistry, hematology: Weeks -2, 0, 4, 8, and 12  
HbA1c: Weeks -2, 0, 4, 8, and 12  
FPG: Weeks 0, 4, 8, and 12  
TSH, T3, T4: Weeks 0 and 12  
Serum hCG (pregnancy): Weeks -2 and 12
- 3) CHP levels may be analyzed in a subset of subjects if residual serum and/or plasma samples are available after completion of protocol-required tests.
- 4) Subjects will be advised to maintain similar exercise and eating habits 3 days prior to the OGTT. Each subject will be instructed not to take his or her usual oral medications or insulin injection and food at least 12 hours before coming to the clinical site between 7:00 am and 8:30 am for an OGTT. Each subject will be allowed to drink only water during the 12-hour fasting period prior to the OGTT and advised not to consume any food. Initial blood will be drawn (15 min prior to OGTT) for serum chemical analysis. The subject will then consume a glucose solution (75 g), followed by one drop of blood drawn for glucose measurements with a glucometer at 0, 0.5, 1.0, 1.5, 2.0, 2.5 and 3 h in the clinical site.
- 5) Assess hypoglycemic & hyperglycemic episodes at Visits 2 to 8 only.

## 3.2 Study Population

### 3.2.1 Inclusion Criteria

To be enrolled in the study, a subject must meet all of the following criteria:

- 1) Males or females aged 18 or older.
- 2) Subjects diagnosed with type 2 diabetes mellitus according to the American Diabetes Association (ADA) criteria.
- 3) Subjects treated with stable doses of insulin and/or other hypoglycemic agent(s) for type 2 diabetes mellitus for at least 2 months prior to randomization.
- 4) Subjects whose fasting blood glucose levels are reasonably stable for at least 2 months prior to randomization and during the 2-week screening period. Stable glucose levels are defined based on the fact that the study subjects did not change the dose and/or type of insulin injection and/or other hypoglycemic agent(s) during the last 2 months and during the 2-week screening period to adjust blood glucose.
- 5) Subjects who have Hemoglobin A1c levels of 7.5 to 10.0 % at Screening.
- 6) Subjects whose BMI is 30 or above.
- 7) Subjects who can give written informed consent.

### 3.2.2 Exclusion Criteria

A subject must not be enrolled in the study if any of the following criteria are met:

- 1) Subjects who have any DM-related end-organ damages.
- 2) Subjects who have a history of diabetic ketoacidosis or hyperosmolar non-ketotic coma.
- 3) Subjects who have any disease likely to limit life span and/or increase risks of interventions such as:
  - Carotid B-mode ultrasound test results indicating clinically significant stenosis in the common carotid arteries requiring intervention by angioplasty or resection.
  - Cancer treatment in the past 5 years, with the exception of cancers which have been cured, and carry a good prognosis.
  - Infectious disease: HIV positivity, active tuberculosis, or pneumonia.
- 4) Subjects who have any of the following conditions related to cardiovascular disease:
  - Hospitalization for the treatment of heart disease in the past 12 months.
  - New York Heart Association Functional Class > 2.
  - Left Bundle branch block on ECG at Screening.
  - Third degree atrioventricular block on ECG at Screening.
  - Uncontrolled hypertension with average systolic blood pressure of > 160 mmHg or diastolic blood pressure > 95 mmHg at Screening and Baseline.
  - Pulse rate > 95 beats per minute at Screening and Baseline.
  - Stroke or transient ischemic attack in the past 12 months.
- 5) Subjects who have any of the following conditions related to gastrointestinal disease:
  - Chronic hepatitis or cirrhosis.
  - Episode of alcoholic hepatitis or alcoholic pancreatitis in the past 2 months.
  - Inflammatory bowel disease requiring treatment in the past 12 months.

- Significant abdominal surgery (e.g., gastrectomy, gastric bypass) in the past 2 months.
- 6) Subjects who have serum creatinine > 1.5 mg/dL for male or > 1.4 mg/dL for female.
- 7) Subjects who have chronic obstructive airway disease or asthma requiring daily therapy or home use oxygen.
- 8) Subjects who have hematocrit < 36.0% for male or < 33.0% for female.
- 9) Subjects who have any of the following conditions or behaviors likely to affect the conduct of the study:
  - Weight loss of > 10% in the past 6 months.
  - Unable to walk without assisted device.
  - Major psychiatric disorder which would impede conduct of the research.
  - Excessive alcohol intake (i.e., more than 2 drinks/day).
- 10) Subjects who take any of the following medications:
  - Psychoactive agents such as monoamine oxidase inhibitors and antidepressants (e.g., lithium, Prozac, Zoloft, Serzone, Paxil, Effexor).
  - Any other medications that may pose harm to the subject.
- 11) Female subjects who have a positive serum pregnancy test at Screening, plan a pregnancy during study period, or are breast feeding.
- 12) Female subjects who don't meet any of the following criteria:
  - Surgically sterile (i.e., have had bilateral tubal ligation, hysterectomy, or bilateral oophorectomy) at least 6 months before randomization.
  - Post-menopausal for at least 12 months prior to Screening.
  - If sexually active, they should use oral contraceptives, double barrier contraception (e.g., condom with spermicide), intrauterine device, or other methods approved by the Sponsor.

### 3.3 Sample Size Considerations

This is a Phase 2 clinical trial to evaluate safety and explore the potential efficacy of the study drug. Therefore, the number of subjects was not based on formal statistical power considerations. In this clinical trial, a total of 64 subjects was deemed sufficient and will be enrolled and randomly assigned to be administered with 1 of 3 dose levels of Cyclo-Z or placebo.

### 3.4 Randomization and Blinding

#### 3.4.1 Randomization

At Visit 2 (Week 0), subjects who meet the inclusion/exclusion criteria will be randomly assigned to receive placebo or 1 of 3 doses of Cyclo-Z in accordance with the randomization code, which will be generated by other Bio-statistics associate (BSA) at MediHelpline rather than the BSA in charge. Specifically, the subjects will be randomly assigned in a 1:1:1:1 ratio to the following:

- Dose A: Cyclo-Z containing 23 mg zinc plus 3 mg CHP – 16 subjects
- Dose B: Cyclo-Z containing 23 mg zinc plus 9 mg CHP – 16 subjects
- Dose C: Cyclo-Z containing 23 mg zinc plus 15 mg CHP – 16 subjects
- Dose D: Placebo – 16 subjects

### 3.4.2 Blinding

As this is a double-blind study, blinding of the drug contents from the subjects, Investigator, and other study personnel at each site is necessary. The subject will be assigned with an identification number at Visit 2 which will remain with the subject throughout the study.

A code-break document including the randomization code information will be retained by each site and can be opened, revealing the randomization information, for emergency purposes only. The Investigator should note that the occurrence of a SAE should not routinely precipitate immediate unblinding. An attempt to contact the Sponsor must be made prior to unblinding. If unblinding occurs, the study medication for the subject must be discontinued; a written explanation on the relevant form must be prepared immediately.

## 4. STUDY ENDPOINTS AND COVARIATES

### 4.1 Primary Endpoints

The primary clinical efficacy variables used to evaluate the efficacy of Cyclo-Z are:

- Change of HbA1c level from baseline at Week 12
- Change of body weight (BW) from baseline at Week 12

### 4.2 Secondary Endpoints

The secondary clinical efficacy variables used to evaluate the efficacy of Cyclo-Z are:

- Change of fasting plasma glucose (FPG) level from baseline at Week 12
- Proportion of subjects achieving HbA1c goal of < 7.0% at Week 12
- Proportion of subjects achieving HbA1c goal of < 6.5% at Week 12
- Change in waist circumference from baseline at Week 12
- Change of postprandial (2 hours after dinner) blood glucose level from baseline at Week 12
- Change of OGTT from baseline at Week 12
- Change of score in Audit of Diabetes-Dependent Quality of Life (ADDQoL) Questionnaire from baseline at Week 12

### 4.3 Exploratory Endpoints

In addition to the primary and secondary endpoints, the following exploratory efficacy variables will be separately evaluated for the change from baseline at Week 12:

- Thyroid Function Test: Thyroid Stimulating Hormone (TSH), Triiodothyronine (T3) and Thyroxine (T4)
- Serum Parameters: zinc, insulin, adiponectin, C-peptide, leptin and glucagon
- Urine Parameters: zinc, glucose, microalbumin and copper
- Three-hour-area-average Above Fasting Glucose Concentration (TAFGC)
- Body Mass Index (BMI)

#### 4.4 Safety Endpoints

The following safety parameters will be evaluated for the change from baseline assessment:

- Blood samples for complete laboratory evaluation
- ECG evaluation
- Physical examination
- Vital signs
- Adverse events
- Episodes of hypoglycemia and hyperglycemia

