## 10.6 Safety Analyses

Safety analysis will be performed based on data of safety analysis set. Safety variables will be summarized with descriptive statistics, overall and by each of the four groups, separately. Continuous safety variables will be summarized with mean, standard deviation, median, 25th & 75th percentiles, minimum, and maximum. Categorical safety variables will be summarized with count and percentage.

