#### 10.6.2 Laboratory Test Results

- Laboratory tests are:
  - Hematology: RBC, WBC, Neutrophil count, Lymphocyte count, Monocyte count, Eosinophil count, Basophil count, Hematocrit, Hemoglobin, Platelets, MCH, MCHC, MCV, and RDW
  - Chemistry: ALT, Albumin, Alkaline phosphatase, AST, Total Bilirubin, BUN, Calcium, Bicarbonate, Chloride, Creatinine, Potassium, Total Protein, Sodium, and Glucose
- Laboratory test results will be collected at V1, V2, V4, V6, and V8. These variables will be summarized with mean, standard deviation, median, 25th & 75th percentiles, minimum, and maximum by each treatment group and by each visit separately.
- Normality of laboratory test results [Normal, Abnormal (CS, NCS)] will be summarized with count (number of subjects) and percentage by each treatment group and by each visit separately.

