#### 10.6.3 Vital Signs

- Vital signs [Sitting blood pressure (systolic, diastolic), Heart rate, Breathing, and Temperature] will be collected at V1, V2, V3, V4, V5, V6, V7, V8, and V9. These variables will be summarized with mean, standard deviation, median, 25th & 75th percentiles, minimum and maximum by each treatment group and by each visit separately.

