#### 10.6.4 Physical Examination and 12-lead ECG

- Result of physical examination (General Appearance, Head-Ears-Eyes-Nose-Throat, Neck, Heart, Lungs, Abdomen, Lymph Nodes, Genitourinary, Extremities, Neurological, Skin, Musculoskeletal, and Others) will be collected at V1, V2, V4, V6, and V8. These results (Normal, Abnormal) will be summarized with count (number of subjects) and percentage by each treatment group and by each visit separately.
- Result of 12-lead ECG will be collected at V1 and V8. This result [Normal, Abnormal (CS, NCS)] will be summarized with count and percentage by each treatment group and by each visit separately.

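### Safety is declared as change from baseline, but the planned lab, vital-sign, ECG and examination tables are by visit only, so within-subject change and new abnormalities do not show in the summaries

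*SAP*

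**What the plan says.** SAP 4.4 lists labs, ECG, physical examination, vital signs, adverse events and glycemic episodes under one lead-in: "The following safety parameters will be evaluated for the change from baseline assessment". Protocol 3.3 uses the same lead-in.

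The analysis sections read as follows.

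- SAP 10.6, for all safety variables: "Safety variables will be summarized with descriptive statistics, overall and by each of the four groups, separately".
- SAP 10.6.2, labs: "Laboratory test results will be collected at V1, V2, V4, V6, and V8". Values are summarized per arm and visit, and for the categories, "Normality of laboratory test results [Normal, Abnormal (CS, NCS)] will be summarized with count (number of subjects) and percentage by each treatment group", again visit by visit.
- SAP 10.6.3, vital signs: "These variables will be summarized with mean, standard deviation, median, 25" and so on to "minimum and maximum by each treatment group and by each visit separately". There is no abnormality category.
- SAP 10.6.4, physical examination: Normal or Abnormal counts per arm and visit.
- SAP 10.6.4, ECG, recorded at V1 and V8 only: "This result [Normal, Abnormal (CS, NCS)] will be summarized with count and percentage by each treatment group and by each visit separately".

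The protocol's own analysis text has the same form. The synopsis plans descriptive summaries per arm and visit, and Protocol 8.1.6 lists means, standard deviations, medians, ranges, counts and percentages. SAP 6 defines baseline as a Week 0 measurement. SAP 13, which lists departures from the protocol, is silent on this point.

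**The concern.** The endpoint section promises a within-subject comparison and the analysis sections deliver cross-sections. A by-visit count of abnormal results does not separate a subject who entered the trial abnormal from one who became abnormal on treatment, and a resolved case can cancel a new one in the total. The denominator also changes as subjects leave, and SAP 13 plans no imputation for safety.

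Safety is the secondary objective, and both Protocol 8.1.6 and SAP 10.6 rule out between-arm tests on it. Apart from the adverse-event tables, these descriptive summaries are what a reader will use to judge whether any dose moves laboratory values, vital signs or ECG findings.

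**Working it through.** **1. Text check.** The documents give no figure to reproduce, so the first step compares each declared measure with its planned summary.

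| Measure | Declared (Protocol 3.3, SAP 4.4) | Planned (SAP 10.6.2 to 10.6.4) | Week 0 value? |
|---|---|---|---|
| Labs | change from baseline | values and Normal / Abnormal (CS, NCS) counts by visit | yes (V2) |
| Vital signs | change from baseline | values by visit, no category | yes (V2) |
| Physical examination | change from baseline | Normal / Abnormal counts by visit | yes (V2) |
| ECG | change from baseline | Normal / Abnormal (CS, NCS) counts at V1 and V8 | no |

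No section plans a change value, a shift table or a count of newly abnormal subjects for any row. By contrast, SAP 10.5.1 and 10.5.2 name the change from baseline for every continuous primary and secondary efficacy endpoint.

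**2. Category counts.** Arm size is n = 64/4 = 16 (SAP 3.3 and 3.4.1). The documents give no abnormality rates, so the counts below are assumed, with every subject measured at both visits. With b abnormal at baseline and f abnormal at Week 12, the number newly abnormal lies between max(0, f − b) and min(f, n − b).

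| b | f | Newly abnormal | Share of the n − b normal at baseline |
|---|---|---|---|
| 4 | 4 | 0 to 4 | 0/12 to 4/12 = 0% to 33.3% |
| 8 | 8 | 0 to 8 | 0/8 to 8/8 = 0% to 100% |
| 4 | 6 | 2 to 6 | 2/12 to 6/12 = 16.7% to 50.0% |
| 0 | 4 | exactly 4 | 4/16 = 25.0% |

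Within each row the planned table looks the same at both ends of the range. The ambiguity depends on the baseline count: with nobody abnormal at baseline there is none.

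**3. Continuous values.** If the same subjects contribute at both visits, the mean change is the difference of the two visit means, so the planned tables do contain it. The spread of the change is not contained. With equal SD at both visits and within-subject correlation ρ, SD(change) = SD × √(2(1 − ρ)). Over assumed values of ρ, the ratio SD(change)/SD is:

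- ρ = 0: √2 = 1.41
- ρ = 0.5: √1 = 1.00
- ρ = 0.9: √0.2 = 0.45

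The by-visit SDs carry no information on ρ. Once subjects drop out, the difference of visit means also ceases to be the mean change in a fixed set of subjects.

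**4. ECG reference.** SAP 6 ties baseline to Week 0, and the schedule has ECG at screening and Week 12 only. Under the SAP's own definition ECG has no baseline, so a change from baseline cannot be formed until a reference visit is named.

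**The case against.** The strongest case against has five parts.

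- **Other routes exist.** A reader might infer that newly abnormal subjects will be invisible in the trial's output. The documents do not support that. SAP 11 plans individual listings. Protocol 9.3.6 requires clinically relevant lab abnormalities to be reported as adverse events, and SAP 10.6.1 summarizes events that start or worsen once dosing has begun, which is itself a before-and-after criterion. This stands and limits the point to the summary tables. The routes do not close the gap: a listing is not an arm-level summary, and adverse-event capture rests on the investigator's judgment of relevance.
- **The SAP follows the protocol.** A reader might infer that the SAP dropped a planned analysis. It did not, because the synopsis and Protocol 8.1.6 already use the descriptive, by-visit form. The mismatch lies between the endpoint section and the analysis section, and both documents contain it. The lead-in also covers adverse events and glycemic episodes, to which change from baseline does not naturally apply, so it may be loosely worded. For the four measures here the phrase has a plain meaning and should be honored or removed.
- **Mean change is partly recoverable.** This is true for labs and vital signs with complete data. The spread of the change, and a matched set of subjects after dropout, are not recoverable.
- **The example is hypothetical.** This stands. The entry criteria exclude several abnormalities and allow others: the ECG exclusions name only left bundle branch block and third-degree AV block. Nothing in the documents shows how many subjects will enter abnormal.
- **The tables will be sparse.** There are 28 lab parameters and 13 examination categories in four arms of 16. This is a fair reason to keep the additions compact, but it does not justify omitting them.

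**Conclusion.** The point holds for the planned summary tables. As written, the plan does not summarize within-subject change for labs, vital signs, ECG or physical examination, although both documents declare that measure. Its category counts do not in general separate abnormalities present at entry from new ones. For vital signs the gap is change only, because they have no abnormality category.

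The size depends on baseline abnormality rates that the documents do not give. Under the assumed counts, the uncertainty in an arm of 16 runs from none (0 then 4 abnormal) to the whole range of 0 to 8 new cases (8 at both visits).

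This is a defect of safety reporting that is cheap to repair. The needed data are collected and listed, and no efficacy result, alpha level or sample size depends on it.

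**What to change.** Amend SAP 10.6 as follows, on the Safety Analysis Set and by arm.

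- **10.6.2 and 10.6.3:** add change-from-baseline summaries by visit for each laboratory parameter and each vital sign.
- **10.6.2:** add shift tables (Normal, Abnormal NCS, Abnormal CS) from baseline to the worst on-treatment category and to Week 12.
- **10.6.4, physical examination:** add a Normal-to-Abnormal shift from baseline.
- **10.6.4, ECG:** add a shift from V1 to V8, and name V1 as the ECG reference in SAP 6, since baseline there means Week 0 and no Week 0 ECG is taken. State also where an ECG from an early-termination visit belongs, because SAP 9.4 maps such visits to the nearest scheduled one and the ECG table has only V1 and V8.
- **SAP 13:** record these additions.

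The cost is SAP wording, one reference-visit definition and a set of additional standard tables from data already collected. Some cells will be sparse at 16 per arm. No visit, procedure or efficacy analysis changes.
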